11.2.3 Sensitivity Analyses of the Primary Efficacy Endpoint

The following sensitivity analyses for the primary endpoint will be performed using the full analysis set:

- The primary analysis will be repeated with all subjects categorized as responders/non-responders based on observed MBL volume data only (without taking into account their reasons for premature discontinuation of study drug).
- The primary analysis will be repeated using the total MBL volume collected from validated products only. All subjects will be categorized as responders/non-responders in the same manner as done in the primary analysis (i.e., subjects who prematurely discontinue study drug due to "lack of

efficacy," "requires surgery or invasive intervention for treatment of uterine fibroids," or adverse events will be considered as non-responders) with exception that all AH data are based on the total MBL volume collected from validated products only.

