### **Sanitary Product Collection for Alkaline Hematin Assay**

Quantitative measurement of the volume of MBL will be performed using the alkaline hematin method. Menstrual blood loss will be assessed in all subjects using validated sanitary products, also referred to as "validated" products. Validated products have undergone analytical testing by the analytical lab to confirm adequate precision and

accuracy of blood recovery as well as no or limited interference with the alkaline hematin method.

Subjects will continue to collect their sanitary products throughout the 6-Month Treatment Period and up through their first menses with full menstrual flow in the Post-Treatment Follow-Up Period to assess return to menses. Subjects will be dispensed sanitary collection kits that consist of validated sanitary products, product collection bags, bar-coded labels and a keg with screw-on lid for storage as provided by the vendor. It is important that only the sanitary products provided for use during the study are used.

[figure not shown]
Validated sanitary products may include:

- Tampax tampons (Regular, Super or Super-Plus absorbency)
- Stayfree Maxi Pads (Regular, Super Long or Overnight absorbency)
- Carefree Original Long Unscented pantliners

Subjects will be required to collect and retain all sanitary products on days with menstrual bleeding or spotting (**subjects must be instructed to collect and return all used or worn products even if there is no visible blood on the products or if non-validated products were used**) as described in the Alkaline Hematin Laboratory Manual.

The dispensation and collection requirements in the Treatment and Post-Treatment Follow-Up Periods are outlined in [Figure 4](#).

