### Use of Non-Validated Products

All subjects are to only use validated products, however, in cases when a subject used non-validated (a product not provided for use in the study), the subject should be instructed to collect and submit the non-validated products to the Study Site.

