7.6 Definitions and Conventions of MBL Volume and Bleeding Days

7.6.1 MBL Volume

The MBL volume is based on validated and non-validated sanitary products unless otherwise specified (for some sensitivity analysis, the MBL volume will be based on validated sanitary products only).

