11.2 Primary Efficacy Analysis

11.2.1 Primary Efficacy Endpoint

The primary endpoint will be the percentage of responders, defined as subjects meeting the following two conditions:

- MBL volume < 80 mL at the Final Month (the last 28 days of treatment), and
- 50% or greater reduction in MBL volume from Baseline to the Final Month (the last 28 days of treatment)

Subjects who prematurely discontinue study drug due to "lack of efficacy," "requires surgery or invasive intervention for treatment of uterine fibroids," or adverse events will be considered as non-responders, regardless if the two conditions above are met or not. Only primary discontinuation reason is considered.

Baseline MBL volume is defined in Section 7.1.

Final Month is defined as in Section 7.2. If a subject has less than or equal to 28 days of treatment, then the Final Month will be the interval between Day 1 to the last dose date.

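### The validated-products-only run in SAP 11.2.3 cannot reveal under-recovered blood on non-validated products, and its baseline and missing-data rules are not settled

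*SAP*

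**What the plan says.** SAP 7.6.1 sets the rule for the primary analysis: "The MBL volume is based on validated and non-validated sanitary products unless otherwise specified". It allows an exception: "for some sensitivity analysis, the MBL volume will be based on validated sanitary products only".

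SAP 11.2.1 requires a responder to meet two conditions. One is a Final Month volume under 80 mL. The other is "50% or greater reduction in MBL volume from Baseline to the Final Month (the last 28 days of treatment".

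SAP 11.2.3 lists two sensitivity analyses. The first ignores the reason for stopping study drug. The second reads "The primary analysis will be repeated using the total MBL volume collected from validated products only" and keeps the discontinuation rule, "with exception that all AH data are based on the total MBL volume collected from validated products only".

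The protocol explains what validation means (5.3.1.1, Sanitary Product Collection for Alkaline Hematin Assay): "Validated products have undergone analytical testing by the analytical lab to confirm adequate precision". The same sentence goes on to accuracy of blood recovery and to interference with the assay. When a woman has used another product, "the subject should be instructed to collect and submit the non-validated products to the Study Site", so that blood is collected.

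Three other places bear on the point:
- Protocol 8.1.7.1.1 gives one definition of MBL volume for the primary and the sensitivity analyses, and it includes both product types.
- Protocol 8.1.7.1.4 says the sensitivity analyses will vary the handling of discontinued subjects and of missing Final Month volume. It does not mention product type.
- SAP 7.1 takes baseline MBL from the pivotal study for every subject. It does not say whether baseline is recomputed on validated products for this run.

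**The concern.** The natural doubt about a non-validated product is whether the assay reads its blood correctly. The reading could be too low (incomplete recovery) or too high (interference). For a claim of reduced bleeding, the harmful error in the Final Month is a reading that is too low: true loss exceeds measured loss, and some women counted as responders are not.

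The planned run does not challenge that error. It takes the doubtful volume out and lets it count for nothing, which moves the Final Month total further in the favourable direction.

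It is also one of only two sensitivity analyses of the primary endpoint. The other lifts the rule that certain discontinuers are non-responders, which can only keep or raise the rate. With baseline unchanged, and among women who have a value, neither planned analysis can lower the primary result. A rate at or slightly above the primary could then be read as evidence that the choice of products does not matter, although the run could hardly have shown otherwise.

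**Working it through.** The documents state no figure for this analysis, so there is none to reproduce. The check is algebra, followed by illustrations on assumed inputs.

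**Notation.** F and B are the all-product Final Month and baseline volumes. f and b are the shares of each on non-validated products. The thresholds (80 mL and 50%) come from SAP 11.2.1. The documents give neither f nor b.

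**1. The 80 mL criterion.** Validated-only volume is F(1 − f), which never exceeds F. The condition F(1 − f) < 80 is the same as F < 80/(1 − f).

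| f | All-product volume that still passes |
|---|---|
| 5% | below 84.2 mL |
| 10% | below 88.9 mL |
| 25% | below 106.7 mL |
| 50% | below 160 mL |
| 75% | below 320 mL |

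The limit is never under 80 mL. A woman who has a validated-only value cannot go from pass to fail.

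**2. The 50% criterion, baseline unchanged.** The condition becomes F ≤ 0.5·B/(1− f). This is also never stricter than F ≤ 0.5·B.

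**3. The 50% criterion, baseline also validated-only.** The condition becomes F ≤ 0.5·B·(1 − b)/(1 − f), which is stricter whenever b > f.
- Stricter: B = 120 mL, b = 50%, f = 0. The limit on F falls from 0.5 × 120 = 60 mL to 0.5 × 120 × 0.5 = 30 mL. A woman at 40 mL is a primary responder and becomes a non-responder.
- Looser: B = 240 mL, b = 0, f = 25%. The primary limit is min(80, 120) = 80 mL. It becomes min(106.7, 160) = 106.7 mL.

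**4. All Final Month blood on non-validated products (f = 100%).** SAP 7.6.1.1 fills days without alkaline hematin data with 0 if some data were observed between the two visits. Otherwise the window is missing unless the UBQ supplies a zero. The SAP does not say whether a keg of excluded products still counts as observed data. The UBQ is completed only when no keg is returned (Protocol Appendix C, Treatment Period footnote on the UBQ), so it is not a fallback for that visit. She becomes either 0 mL or missing.

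**5. Illustrative size of the planned run.** Assumptions: 400,000 simulated women; baseline 80 mL plus a gamma variable (shape 1.5, scale 100); 45% with zero Final Month loss, the rest lognormal (3.3, 1.3); users of non-validated products lose a share drawn evenly from 0 to 80%; use at baseline and in the Final Month is independent.

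| Users (assumed) | 80 mL criterion met | Composite, baseline unchanged | Composite, baseline also validated-only |
|---|---|---|---|
| none (primary) | 88.90% | 87.64% | 87.64% |
| 5% | 89.17% | 87.93% | 87.64% |
| 15% | 89.65% | 88.44% | 87.60% |
| 30% | 90.43% | 89.29% | 87.66% |

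No woman was lost in the first two result columns. In the last, gains and losses nearly cancel (at 30% users, 1.45% gained and 1.43% lost).

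**6. Illustrative size of a worst-case run.** Count users who bled as non-responders. Women with zero loss are all responders, so responders who bled make up 87.64% − 45% = 42.64% of the total. The rate falls by 2.1 points at 5% users (0.05 × 42.64), 6.4 at 15% and 12.8 at 30%. A second assumed set (60% with zero loss, primary rate 81.0%) gives 81.0% − 60% = 21.0%, hence a fall of 1.05 points at 5% users and 4.2 at 20%. Among women who bled, the first set has a responder rate of 42.64/55 = 77.5%, below the overall 87.64%. Simply dropping bleeders would therefore raise the rate.

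**The case against.** The strongest reply has four parts.

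- **Interference is a real concern.** The protocol names it beside recovery. If non-validated products inflate readings, leaving them out is a reasonable one-sided check. This stands. A reader might infer that the run cannot test any measurement doubt, or that the validated-only volume is known to be too low; the documents support neither. The valid claim is limited to under-recovery.
- **The result need not sit at or above the primary.** A reader might infer that it must. Read literally, the SAP's wording on alkaline hematin data is not limited to the Final Month. If baseline shrinks too, the composite can fall, as step 3 shows. A primary responder with only non-validated products may also drop out as missing. This stands, but it shows that the direction of the run depends on rules the SAP does not state.
- **Purpose and authority.** Neither document says what this analysis is for, so a measurement purpose is an inference from the only distinction the protocol draws between product types. Protocol 8.1.7.1.4 also leaves the details of sensitivity analyses to the SAP. That softens the conflict with Protocol 8.1.7.1.1 but does not remove it, because 8.1.7.1.1 fixes the volume for both kinds of analysis.
- **The effect may be small.** Women are supplied with validated products and told to use only those, and efficacy is descriptive without tests. This stands. It is a reason to report the number of users, which would settle the matter.

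**Conclusion.** The point holds in a limited form. For any woman with a validated-only value, the run can only relax the 80 mL criterion. With baseline unchanged it can only relax the 50% criterion too. It therefore cannot reveal under-recovery on non-validated products. This is algebra and needs no assumption about usage.

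Two rules are missing: whether baseline is restricted, and what happens to a woman with only non-validated products. The SAP wording also conflicts with Protocol 8.1.7.1.1.

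The size is unknown. On the assumed inputs in step 5, with baseline unchanged, the planned run raises the composite by 0.29 to 1.65 points (5% to 30% users). A worst-case run would lower it by 1.05 to 12.8 points across both assumed sets. These figures show direction and scale only; if use is rare, both shrink towards zero. The primary estimate itself is not affected. What is missing is a check in the unfavourable direction.

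**What to change.** In SAP 11.2.3:

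1. Add a run on the all-product volume, with baseline as in the primary analysis. Women with measurable blood (> 0 mL) on non-validated products in the Final Month have that month's volume set to missing, handled as the primary analysis handles missing volume. SAP 11.2.2 reports as observed while Protocol 8.1.7.1.3 describes multiple imputation, so name the method.
2. Add a worst-case run that counts the same women as non-responders. It is needed because the first run may raise the rate by dropping women who bled. The > 0 mL condition matters: women must return unstained products too, and one unstained non-validated liner should not make a woman a failure.
3. Report the number of such women per analysis group.
4. Keep the validated-only run only if it is labelled a lower bound on Final Month blood loss, uses all-product baseline, and treats women with only non-validated products as missing, not 0 mL.
5. Reconcile SAP 11.2.3 with the definition in Protocol 8.1.7.1.1.

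The cost is SAP wording and a little more programming. Runs 1 and 2 need volumes by product type, which the planned run already requires, so no new data collection follows. The downside is a worst-case rate somewhat below the primary, by an amount that depends on usage.

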11.2.4 Adenomyosis Subset

The proportion of responders will be summarized by analysis group for subjects with Baseline adenomyosis present, and repeated for the subjects with adenomyosis at any time during the Baseline or Treatment Period (see definition in Section 11.3.5.3).

11.3 Secondary and Other Efficacy Analyses

Secondary efficacy endpoints during the Treatment Period include the following:

- Change and percent change from Baseline in MBL volume to each month and to the Final Month;
- Percentage of subjects with suppression of bleeding (no bleeding allowed, spotting allowed) at the Final Month;
- Percentage of subjects with Baseline hemoglobin ≤ 10.5 g/dL who have an increase in hemoglobin > 2 g/dL at Month 6.

Other efficacy endpoints during the Treatment Period include the following:

- Percentage of subjects with MBL volume < 80 mL and 50% or greater reduction in MBL volume from Baseline during 28-day intervals throughout the Treatment Period;
- Percentage of subjects with amenorrhea;
- Percentage of subjects with control of bleeding;
- The number of bleeding days;
- Change and percent change from Baseline in hemoglobin concentration;
- Patient Global Impression of Change (PGIC) questionnaire for Menstrual Bleeding and Non-Bleeding Uterine Fibroid Symptoms;

- Change and percent change from baseline in fibroid and uterine volume;
- Change from baseline for the UFS-QoL;
- Change from baseline for the EuroQoL-5D (EQ-5D-5L);
- The Health Care Resource Utilization (HCRU) questionnaire;
- Change from baseline for the WPAI.

11.3.1 Reduction of Bleeding

The change and percent change from Baseline to the observed Final Month in MBL volume will be summarized by analysis group.

The change and percent change from Baseline to each 28-day window starting at Study Day 1 up to Study Day 168 in observed MBL volume in the Treatment Period (i.e., Month 1 (Study Days 1 - 28), Month 2 (Study Days 29 - 56), Month 3 (Study Days 57 - 84), Month 4 (Study Days 85 - 112), Month 5 (Study Days 113 - 140), and Month 6 (Study Days 141 - 168)) will be summarized by analysis group. For observed MBL volume in each 28-day interval, only subjects who did not prematurely discontinue in or before this 28-day interval will be included. For example, for Study Days 29 - 56, it includes subjects who were on treatment for at least 56 days.

Each of the two response criteria that are components of the primary endpoint, i.e., (1) MBL volume of < 80 mL at the Final Month; and (2) 50% or greater reduction in MBL volume from Baseline to the Final Month will be summarized separately in the same way as for the primary analysis. The number and percentage of subjects meeting each criterion at the Final Month will be summarized by analysis group.

The number and percentage of subjects meeting each criterion at the Final Month will also be analyzed in the same way as in each sensitivity analysis for the primary endpoint, and in the analysis for subjects identified in the adenomyosis subset of interest.

The number and percentage of subjects satisfying either (1) MBL volume < 80 mL, or (2) 50% or greater reduction in MBL volume from Baseline, or both will be summarized for every 28-day interval by analysis group based on observed MBL volume.

Plots will be provided by analysis group using the observed MBL volume data:

- Cumulative distribution function for MBL volume at Final Month;
- Cumulative distribution function for percent change from Baseline to Final Month in MBL volume;
- Proportion of responders at Final Month;
- Cumulative distribution function for change from baseline to Final Month in MBL volume.
- Cumulative distribution function for change from baseline in MBL volume to each month;
- Mean change in MBL volume over time.

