**Analyses for Secondary and Other Efficacy Variables:**

The change and percent change from baseline in MBL volume to each month and to the Final Month will be summarized for each treatment group. The percentage of subjects with MBL volume < 80 mL and 50% or greater reduction in MBL volume from baseline to each month in the Extension Study will be summarized by treatment group. The percentage of subjects with suppression of bleeding and the percentage of subjects with amenorrhea will be summarized by treatment group.

The change and percent change from baseline to the Month 6 in the Extension Study in hemoglobin concentration will be summarized by treatment group.

The change and percent change from baseline in primary fibroid volume, total fibroid volume, and uterine volume will be summarized for each treatment group.

The change from baseline for Quality of Life assessments (e.g., UFS-QoL, EQ-5D-5L) will be summarized for each treatment group. For the PGIC-MB and PGIC-NBUFS, the number and percentage of subjects in each response category will be summarized by treatment group.

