### **Definition of Terms**

Pivotal Study	Studies M12-815/M12-817: A Phase 3 Study to Evaluate the Efficacy and Safety of Elagolix in Combination with Estradiol/Norethindrone Acetate for the Management of Heavy Menstrual Bleeding Associated with Uterine Fibroids in Premenopausal Women.
Extension Study	Study M12-816: Extension Study to Evaluate the Efficacy and Safety of Elagolix in Premenopausal Women with Heavy Menstrual Bleeding Associated with Uterine Fibroids.
Day 1 or Treatment Period Day 1	The day a subject takes her first dose of study drug in this Extension Study M12-816. The Day 1 Visit will occur only after completing Treatment Period of the Pivotal Studies M12-815/M12-817.
Monthly Visits: Treatment Period Months 1 through 6 and Post-Treatment Period Months 1 through 12	A month is defined as 28 days.
Product Collection Visits	Visits at which subjects return used sanitary products for assessment of alkaline hematin levels (either during Screening or the Treatment Period); visits should occur within approximately 5 days after the last sanitary product was collected during a bleeding and/or spotting episode.
Home Product Collection Visits	Product Collection Visit conducted at home by a Home Health Care Agent who will go to the subject's home to draw a venous blood sample and retrieve the collection keg to return to the study site.
Heavy Menstrual Bleeding	Menorrhagia or > 80 mL blood loss.
Vasomotor Symptoms	Examples: hot flush and night sweats.

2.0	Table of Contents	
1.0	Title Page .....	1
1.1	Protocol Amendment: Summary of Changes .....	2
1.2	Synopsis .....	5
1.3	List of Abbreviations and Definition of Terms .....	14
2.0	Table of Contents .....	18
3.0	Introduction .....	24
3.1	Uterine Fibroids .....	24
3.2	Elagolix .....	25
3.2.1	Preclinical Experience .....	26
3.2.1.1	Toxicology .....	26
3.2.2	Clinical Experience .....	27
3.2.2.1	Pregnancy in Elagolix Studies .....	35
3.3	Estradiol/Norethindrone Acetate .....	40
3.4	Differences Statement .....	41
3.5	Benefits and Risks .....	41
4.0	Study Objective .....	42
5.0	Investigational Plan .....	42
5.1	Overall Study Design and Plan: Description .....	42
5.2	Selection of Study Population .....	48
5.2.1	Inclusion Criteria .....	48
5.2.2	Exclusion Criteria .....	50
5.2.2.1	Concomitant Therapy .....	51
5.2.2.2	Iron Supplementation .....	52

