#### **8.1.7.3.1 Reduction of Bleeding**

The percentage of subjects with MBL volume  $< 80$  mL and 50% or greater reduction in MBL volume from baseline during the Treatment Period in this Extension Study will be summarized for each treatment group. Also, the individual component (the percentage of subjects with MBL volume of  $< 80$  mL as well as the percentage of subjects with  $\geq 50\%$  in MBL volume reduction from baseline) will be summarized.

The change and percent change from baseline in MBL volume to each month and to the Final Month, will be summarized for each treatment group. The percentage of subjects with suppression of bleeding and the percentage of subjects with amenorrhea will be

summarized by monthly intervals throughout the Treatment Period. For each subject, suppression of bleeding will be defined as having no days of bleeding (spotting is allowed) during a 28-day interval. Amenorrhea is defined as having no days of bleeding or spotting during a 28-day interval. In addition, the cumulative percentage of subjects with suppression of bleeding and the cumulative percentage of subjects with amenorrhea will be summarized by treatment group.

The change and percent change from baseline to monthly intervals in number of bleeding days will be summarized by treatment group.

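### SAP 11.3.1 words the 28-day responder summary as meeting either criterion or both, while the listed monthly endpoint requires both

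*SAP*

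**What the plan says.** SAP 11.3 lists, among the other efficacy endpoints, "Percentage of subjects with MBL volume < 80 mL and 50% or greater reduction in MBL volume from Baseline during 28-day intervals". The two criteria are joined by *and*.

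The protocol agrees. Its synopsis, under secondary and other efficacy variables, plans "The percentage of subjects with MBL volume < 80 mL and 50% or greater reduction in MBL volume from baseline to each month". Section 8.1.7.3 lists the endpoint in the same form and leaves analysis details to the SAP. Section 8.1.7.3.1 plans the composite first, again joining the volume criterion by *and* to "50% or greater reduction in MBL volume from baseline during the Treatment Period in this Extension Study will be summarized for each treatment group". Its next sentence begins "Also, the individual component (the percentage of subjects with MBL volume of" and goes on to name each criterion in turn, so the components come in addition to the composite.

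The SAP text that turns this endpoint into a table is in 11.3.1. It asks for a count and a rate of women "satisfying either (1) MBL volume < 80 mL, or (2) 50% or greater reduction in MBL volume from Baseline, or both". The same sentence adds that this tabulation "will be summarized for every 28-day interval by analysis group based on observed MBL volume".

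For the Final Month primary endpoint there is no doubt: SAP 11.2.1 has responders "defined as subjects meeting the following two conditions".

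**The concern.** An inclusive *or* describes the union of the two criteria. The endpoint that the table is meant to deliver is their intersection. The union is easier to meet and is not listed as an endpoint in either document.

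The monthly rates are where a reader would look for the onset and durability of response. If they count women who meet one criterion only, they measure something weaker than the protocol promised. Two programmers working from the same SAP could also produce different tables, one from the list in 11.3 and one from the sentence in 11.3.1.

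**Working it through.** The plan states no monthly rate, so there is no figure to reproduce. The check is one of logic, followed by an illustration of size.

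**Inputs from the documents**
- Criterion 1: MBL below 80 mL in the interval. Criterion 2: a reduction of at least 50% from Baseline (SAP 11.3, 11.3.1).
- Baseline MBL: no distribution is given. The protocol's Definition of Terms describes heavy menstrual bleeding as "Menorrhagia or > 80 mL blood loss", so baselines are taken to exceed 80 mL.
- Phase 2b composite rates (both criteria, Final Month; protocol 3.2.2, Cohort 1): 91.9% on elagolix 300 mg BID alone and 79% with standard-dose E2/NETA. They serve only to set the scale.

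**Step 1: direction**

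P(1 or 2) = P(1) + P(2) − P(1 and 2). This is never below P(1 and 2). The excess is the proportion of women who meet exactly one criterion.

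**Step 2: which women change status**

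For baseline B and interval volume M, criterion 1 is M < 80 and criterion 2 is M ≤ B/2. Meeting both requires M to be under the lower of 80 mL and B/2. Meeting either requires only the higher of the two.

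| B (mL) | B/2 | Cut for both | Cut for either |
|---|---|---|---|
| 100 | 50 | 50 | 80 |
| 160 | 80 | 80 | 80 |
| 200 | 100 | 80 | 100 |
| 300 | 150 | 80 | 150 |

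The cuts coincide only at B = 160 mL. Two examples:
- B = 100, M = 70: reduction (100 − 70)/100 = 30%. Criterion 1 met, criterion 2 not. Not a responder under SAP 11.3; counted under 11.3.1 read literally.
- B = 300, M = 120: reduction (300 − 120)/300 = 60%. Criterion 2 met, criterion 1 not. The same disagreement.

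**Step 3: illustrative size (assumptions, not document figures)**

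Baseline is log-normal, truncated above 80 mL, with median parameter 120 to 300 mL and log-SD 0.5. Between 30% and 65% of women have 0 mL in the interval. For the rest, the ratio of interval volume to baseline is log-normal with log-SD 1.2, centred so that the rate meeting both criteria equals a Phase 2b value. The extremes of the grid are:

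| Both | Baseline median; share at 0 mL | Criterion 1 | Criterion 2 | Either = C1 + C2 − both | Excess (points) |
|---|---|---|---|---|---|
| 79.0% | 120 mL; 65% | 81.6% | 80.2% | 82.8% | 3.8 |
| 79.0% | 300 mL; 30% | 79.2% | 90.6% | 90.8% | 11.8 |
| 91.9% | 120 mL; 65% | 93.4% | 92.9% | 94.4% | 2.5 |
| 91.9% | 300 mL; 30% | 92.0% | 97.6% | 97.7% | 5.8 |

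The range is therefore 2.5 to 11.8 points. Without distributional assumptions, the either-rate can lie anywhere from the both-rate up to 100%.

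**The case against.** The strongest reply is that the sentence was meant as three tabulations: criterion 1, criterion 2, and both. That would match protocol 8.1.7.3.1 and would sit naturally after the Final Month paragraph of SAP 11.3.1, which reports each criterion separately. The endpoint is also listed with *and* wherever it is named, and SAP 7.6.1.1 defines observed MBL volume for Months 1 to 6, so a careful programmer could build the right table from the list alone.

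Much of this stands. The three-table reading is plausible and may be what was intended. But the sentence does not say it. The wording that makes the Final Month components separate is missing from the monthly sentence, which describes a single count joined by *or*. The protocol leaves the detail to the SAP, and this is the only SAP sentence that gives it for the 28-day intervals. Under the benign reading the sentence still needs the same edit.

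The other side is also right that the consequence is small. SAP 11.1 plans no efficacy tests, and the primary endpoint, its components at the Final Month and its sensitivity analyses use separate text.

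**Conclusion.** The inconsistency is real, and its direction is certain if the sentence is followed literally: monthly rates at or above the listed composite. The size cannot be derived from the documents. About 3 to 12 points near composite rates of 79% to 91.9% is an illustration that rests on the assumed baseline spread, the share of women at 0 mL and the log-normal response. It is a minor point about a descriptive summary.

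Three stronger readings are tempting and not supported:
- *The monthly rates will be too high.* That holds only if the sentence is programmed as a union. The three-table reading remains open.
- *The excess could be 6 to 19 points.* A model with no women at 0 mL and composite rates down to 49% gives that. SAP 7.6.1.1 assigns 0 mL to no-bleeding and no-visible-blood reports, amenorrhea is itself an endpoint, and the only composite rates the documents give for these two regimens are 79% and 91.9%.
- *Correcting the sentence makes monthly and primary results one time course.* It does not. SAP 11.3.1 restricts observed MBL in an interval to women who did not discontinue in or before it. SAP 11.2.1 counts discontinuation for adverse events, lack of efficacy or fibroid surgery as non-response. That difference remains.

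**What to change.** Replace the sentence in SAP 11.3.1 with wording such as: *For each 28-day interval and analysis group, using observed MBL volume, report the number and percentage of subjects who meet (a) both response criteria, (b) the 80 mL volume criterion, and (c) the 50% reduction criterion, as three separate tabulations.*

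This restores agreement with SAP 11.3 and the protocol, and it also delivers the three-table version if that was the intent. The cost is one SAP sentence and the matching table shell; it needs no new data and no protocol amendment. A footnote on the monthly table, saying that discontinued women are handled differently from the primary analysis, would keep the two from being read as one series.
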